6. STUDY INTERVENTION(S) AND CONCOMITANT THERAPY

Study interventions are all prespecified investigational and non-investigational products, medical devices, and other interventions (eg, surgical and behavioral) intended to be administered to the study participants during the study conduct.

For the purposes of this protocol, study intervention refers to ponsegromab (PF-06946860, IMP), and placebo (IMP).

Study Interventions Administered

Intervention Name	Ponsegromab (PF-06946860)	Placebo
Arm Name (group of participants receiving a specific treatment or no treatment)	Ponsegromab double-blind treatment	Placebo double-blind treatment
Type	Biologic	Placebo
Dose Formulation	Solution for injection	Solution for injection
Unit Dose Strength(s)	100 mg/mL	Placebo
Dosage Level(s)	100, 200 or 300 mg Q4W	Placebo Q4W
Route of Administration	SC	SC
Use	Experimental	Placebo
IMP or NIMP/AxMP	IMP	IMP
Sourcing	Provided centrally by the sponsor	Provided centrally by the sponsor
Packaging and Labeling	Study intervention will be provided in 6-mL glass vial with an up to 1 mL withdrawal volume. Each vial will be labeled as required per country requirement. Each vial is for single use only.	Study intervention will be provided in 6-mL glass vial with an up to 1 mL withdrawal volume. Each vial will be labeled as

Intervention Name	Ponsegromab (PF-06946860)	Placebo
		required per country requirement. Each vial is for single use only.

	Study Arms for Main Cohort (Cohort A) ^a					
Arm Title	Ponsegromab or Placebo ^b 100 mg		Ponsegromab or Placebo ^b 200 mg		Ponsegromab or Placebo ^b 300 mg	
Arm Type	Experimental n=18	Placebo n=6	Experimental n=18	Placebo n=6	Experimental n=190	Placebo n=178
Arm Description	Participants will receive 100 mg Q4W SC	Participants will receive placebo Q4W SC	Participants will receive 200 mg Q4W SC	Participants will receive placebo Q4W SC	Participants will receive 300 mg Q4w SC	Participants will receive placebo Q4W SC
Associated Intervention Labels	Ponsegromab 100 mg	Placebo	Ponsegromab 200 mg	Placebo	Ponsegromab 300 mg	Placebo

- A total of 6 doses will be administered from Day 1 to Week 20.
- As different volumes are required for the different dose levels of ponsegromab, each study arm will have a volume-matched placebo to maintain blinding within each study arm. Each dose will be administered as 2 SC injections of equal volume. In addition, during SV2, all participants will receive 2 SC injections of open-label placebo (equivalent of highest possible dose, 300 mg) to assess injection tolerability.

	Study Arms for Open-label, PK Cohort (Cohort B) ^{a,b}		
Arm Title	Ponsegromab 100 mg	Ponsegromab 200 mg	Ponsegromab 300 mg
Arm Type	Experimental n=4	Experimental n=8	Experimental n=8
Arm Description	Participants will receive 100 mg Q4W SC	Participants will receive 200 mg Q4W SC	Participants will receive 300 mg Q4W SC
Associated Intervention Labels	Ponsegromab 100 mg	Ponsegromab 200 mg	Ponsegromab 300 mg

- A total of 4 doses will be administered from Day 1 to Week 12.
- If not previously administered, participants will receive 2 SC injections of open-label placebo (equivalent of highest possible dose, 300 mg) during the screening period to assess injection tolerability.

	Study Arms for Cohort C^a	
Arm Title	Ponsegromab or Placebo^b 100 mg	
Arm Type	Experimental n~130	Placebo n~65
Arm Description	Participants will receive 100 mg Q4W SC	Participants will receive placebo Q4W SC
Associated Intervention Labels	Ponsegromab 100 mg	Placebo

- A total of 6 doses may be administered from Day 1 to Week 20.
- Each dose will be administered as 2 SC injections of equal volume. In addition, during SV2, all participants will receive 2 SC injections of open-label placebo (equivalent of highest possible dose, 300 mg) to assess injection tolerability.

	Study Arms for Cohort D^a	
Arm Title	Ponsegromab or Placebo^b 300 mg	
Arm Type	Experimental n~50	Placebo n~50
Arm Description	Participants will receive 300 mg Q4W SC	Participants will receive placebo Q4W SC
Associated Intervention Labels	Ponsegromab 300 mg	Placebo

- A total of 6 doses may be administered from Day 1 to Week 20.
- Each dose will be administered as 2 SC injections of equal volume. In addition, during SV2, all participants will receive 2 SC injections of open-label placebo (equivalent of highest possible dose, 300 mg) to assess injection tolerability.

6.1. Administration

Each dose of investigational product must be administered by appropriately qualified personnel.

Study intervention will be administered in a divided dose requiring 2 separate SC injections given in rapid succession every 4 weeks. The permitted injection sites are the abdomen, upper arm (right or left) and the thigh (right or left). The following combination of injection sites are provided as examples:

- Two injections in the abdomen (each injection should be administered into a different quadrant and separated by at least 3 cm),
- One injection into each upper arm
- One injection into each thigh

- One injection into the arm (right or left) and one injection in the leg (right or left), or
- One injection in arm or leg (left or right) and one in the abdomen.

The injections can be rotated with each administration for participant comfort. If participants are receiving other, non-study intervention injectable agents, those interventions should be administered in a quadrant different from where the study intervention was administered. Additionally, areas with scarring, redness, tattoos, or other visible marks should be avoided.

Please refer to the IP manual for specific instructions on the handling, preparation, and administration of study intervention.

Premedication is permitted for all participants, consistent with institutional guidelines, and may include an antihistamine, anti-inflammatory agent, or pain reliever.

6.2. Preparation, Handling, Storage, and Accountability

1. The investigator or designee must confirm that appropriate conditions (eg, temperature) have been maintained during transit for all study interventions received and any discrepancies are reported and resolved before use of the study intervention.
2. Only participants enrolled in the study may receive study intervention and only authorized site staff may supply, prepare, and/or administer study intervention.
3. All study interventions must be stored in a secure, environmentally controlled, and monitored (manual or automated recording) area in accordance with the labeled storage conditions with access limited to the investigator and authorized site staff. At a minimum, daily minimum and maximum temperatures for all site storage locations must be documented and available upon request. Data for nonworking days must indicate the minimum and maximum temperatures since previously documented upon return to business.
4. Any excursions from the study intervention label storage conditions should be reported to Pfizer upon discovery along with actions taken. The site should actively pursue options for returning the study intervention to labeled storage conditions, as soon as possible. Once an excursion is identified, the study intervention must be quarantined and not used until Pfizer provides permission to use the study intervention. Specific details regarding the excursion definition and information to report for each excursion will be provided to the site in the IP Manual.
5. Any storage conditions stated in the SRSD will be superseded by the storage conditions stated on the label. Site staff will instruct participants on the proper storage requirements for take-home study intervention.
6. Study interventions should be stored in their original containers.

7. The investigator, institution, head of the medical institution (where applicable), or authorized site staff is responsible for study intervention accountability, reconciliation, and record maintenance (ie, receipt, reconciliation, and final disposition records), such as the IPAL or sponsor-approved equivalent. All study interventions will be accounted for using a study intervention accountability form/record. Returned study intervention must not be re-dispensed to the participants.
8. Further guidance and information for the final disposition of unused study interventions are provided in the IP Manual. All destruction must be adequately documented. If destruction is authorized to take place at the investigator site, the investigator must ensure that the materials are destroyed in compliance with applicable environmental regulations, institutional policy, and any special instructions provided by Pfizer.

Upon identification of a product complaint, notify the sponsor within 1 business day of discovery as described in the IP Manual.

6.2.1. Preparation and Dispensing

Investigational Product, ponsegromab (100 mg/mL) and placebo will be prepared in a blinded fashion by qualified personnel according to the IP manual. The study intervention will be administered in a blinded fashion by qualified personnel to the participants. A second staff member will verify the dispensing.

Open-label, PK cohort (Cohort B) only: Open-label ponsegromab will be prepared as per treatment assignment by qualified personnel according to the IPM, and administered by qualified personnel to the participants. A second staff member will verify the dispensing.

6.3. Assignment to Study Intervention

Allocation of participants to treatment groups in Main Cohort (Cohort A), Cohort C and Cohort D will proceed through the use of an IRT system. The site personnel (study coordinator or specified designee) will be required to enter or select information including but not limited to the user's ID and password, the protocol number, and the participant number. Randomization is stratified based on KCCQ-23 CSS score (Main Cohort [Cohort A], Cohort C and Cohort D) and GDF-15 concentrations (Main Cohort [Cohort A] and Cohort C only) from SV1 assessments; these data points will be required to be entered in the IRT system to ensure appropriate randomization allocations.

The site personnel will then be provided with a randomization number corresponding to the assigned treatment group, and DU or container number(s) when study intervention is being supplied via the IRT system. The IRT system will provide a confirmation report containing the participant number, randomization number, and DU or container number assigned. The confirmation report must be stored in the site's files.

Study intervention will be administered at the study visits summarized in the [SoA](#).

The study-specific IRT reference manual and IPM will provide the contact information and further details on the use of the IRT system.

Open-label, PK cohort (Cohort B): This is an open-label cohort; however, the specific treatment assignment (ie, 100 mg, 200 mg, or 300 mg open-label dose arm) will be assigned using the IRT system. Randomization for this cohort is not stratified.

6.4. Blinding (Main Cohort [Cohort A]/Cohort C/Cohort D)

This is a double-blind study, with blinding of ponsegromab versus placebo for each dose level.

6.4.1. Blinding of Participants (Main Cohort [Cohort A]/Cohort C/Cohort D)

Participants and their caregivers will be blinded to their assigned study intervention.

6.4.2. Blinding of Site Personnel (Main Cohort [Cohort A]/Cohort C/Cohort D)

Investigators and other site staff will be blinded to participants' assigned study intervention, including the site staff assigned to prepare and administer the study intervention. Pharmacists and site personnel will be blinded to study intervention versus placebo within each study arm.

6.4.3. Blinding of the Sponsor (Main Cohort [Cohort A]/Cohort C/Cohort D)

Sponsor staff will be blinded to participants' assigned study intervention, except for sponsor staff involved in the assignment or distribution of study intervention.

Sponsor staff who are not directly involved with the conduct of this study will prepare analyses and documentation containing unblinded data while the study is ongoing to support interactions with the E-DMC and IRC as documented in the respective charters.

6.4.4. Breaking the Blind (Main Cohort [Cohort A]/Cohort C/Cohort D)

The IRT will be programmed with blind-breaking instructions. In case of an emergency, the investigator has the sole responsibility for determining if unblinding of a participant's treatment assignment is warranted. Participant safety must always be the first consideration in making such a determination. If the investigator decides that unblinding is warranted, the investigator should make every effort to contact the TIMI Hotline (available 24/7) or the study medical monitor prior to unblinding a participant's treatment assignment unless this could delay further management of the participant. If a participant's treatment assignment is unblinded, the sponsor must be notified within 24 hours after breaking the blind. The date and reason that the blind was broken must be recorded in the source documentation and the CRF.

The study-specific IRT reference manual and IPM will provide the contact information and further details on the use of the IRT system.

6.5. Study Intervention Compliance

The study intervention will be administered to participants directly by an appropriately qualified individual. In this study, participants are dosed at the site, and they will receive study intervention directly from the investigator or designee, under medical supervision. The date and time of each dose administered in the clinic will be recorded in the source documents and recorded in the CRF. The dose of study intervention and study participant identification will be confirmed at the time of dosing by a member of the study site staff other than the person administering the study intervention if the study intervention is administered at the clinic.

The site will complete the required dosage Preparation Record located in the IP Manual. The use of the Preparation Record is preferred, but it does not preclude the use of an existing appropriate clinical site documentation system. The existing clinical site's documentation system should capture all pertinent/required information on the preparation and administration of the dose. This may be used in place of the Preparation Record after approval from the sponsor and/or designee.

Deviation(s) from the protocol-specified dosage regimen should be recorded in the CRF. In exceptional circumstances and with agreement from the Sponsor, the study intervention may be administered outside of the window for a given dosing visit with appropriate consideration of timing of any subsequent dosing visit; in such circumstances, the rationale should be recorded in the CRF.

A record of the number of vials and syringes dispensed to and taken by each participant must be maintained and reconciled with study intervention and compliance records. Intervention start and stop dates, including dates for intervention delays and/or dose reductions, will also be recorded in the CRF.

6.6. Dose Modification

There is no dose modification of ponsegromab anticipated in this study.

6.7. Continued Access to Study Intervention After the End of the Study

No study intervention will be provided to participants at the end of their study participation. It is expected that participants will be treated as required with standard-of-care treatments, as advised by their usual care physician.

6.8. Treatment of Overdose

For this study, any dose of ponsegromab greater than 700 mg within a 4-week period will be considered an overdose.

There is no specific treatment for an overdose.

In the event of an overdose, the investigator should:

1. Contact the study medical monitor or TIMI Hotline within 24 hours.
2. Closely monitor the participant for any AEs/SAEs as medically appropriate and at least until the next scheduled follow-up.
3. Document the quantity of the excess dose as well as the timeframe (eg, frequency) of overdose(s) in the CRF.
4. Overdose is reportable to Pfizer Safety only when associated with an SAE.
5. Obtain a blood sample for PK, GDF-15, and/or immunogenicity analysis within 5-7 days from the date of the last dose of study intervention if requested by the study medical monitor (determined on a case-by-case basis).

Decisions regarding dose interruptions or modifications will be made by the investigator in consultation with the study medical monitor as needed based on the clinical evaluation of the participant.

6.9. Prior and Concomitant Therapy

Participants in this study will be allowed to be on concomitant medications that have been prescribed according to their label. Attempts should be made not to alter the doses and regimens of the background medications after randomization and for the duration of participation in this study, except in circumstances where a change in dose is deemed medically necessary. Any changes must be captured in the CRF. Additionally, many over-the-counter medications are also permitted during this study.

Treatments taken within 56 days in either cohort before the first dose of IP will be documented as prior treatment. Treatments taken after the first dose of IP will be documented as concomitant treatment.

All concomitant treatments, both prescription and over-the-counter taken during the study must be recorded with indication, daily dose, and start and stop dates of administration. All participants will be questioned about concomitant treatment at each clinic visit.

Use of investigational therapies is prohibited during the study. See [Appendix 9](#) for details regarding prohibited concomitant medications due to potential DDI.

Hormonal contraceptives that meet the requirements of this study are allowed to be used in participants who are WOCBP (see [Appendix 4](#)).

Background biologics are permitted as indicated by the label (not contra-indicated for combination with an investigational mAb).

7. DISCONTINUATION OF STUDY INTERVENTION AND PARTICIPANT DISCONTINUATION/WITHDRAWAL

7.1. Discontinuation of Study Intervention

The study intervention **must** be permanently discontinued for the following reasons:

- Severe allergic reaction to study intervention.
- Intent to become pregnant or pregnancy confirmed by β -hCG testing.
- Drug-induced liver injury as described in [Section 10.6](#), [Appendix 6](#), Liver Safety: Suggested Actions and Follow-up Assessments.
- The study participant undergoes heart transplantation or requires mechanical circulatory support.
- The investigator has determined that continuation of the administration of the study intervention is no longer feasible or appropriate.

Other reasons that may prompt consideration for permanent discontinuation of study intervention include the following:

- ECG Findings of potential concern as described in [Section 10.8](#), [Appendix 8](#), ECG Findings of Potential Clinical Concern.
- If a participant experiences serious or severe AEs judged by the Investigator as related to randomized study intervention, the study intervention will be temporarily discontinued until the treatment-related AEs return to a moderate level or less. If the treatment-related AEs return to a moderate level or less, or resolve within 4 weeks, continuation of dosing with study intervention may be considered. If these AEs do not return to moderate within 4 weeks, and after discussion with the TIMI Hotline, the participant will be permanently discontinued from the study intervention.

Any planned or potential discontinuation of study drug should be discussed with the TIMI Hotline (available 24/7). Note that discontinuation of study intervention does not represent withdrawal from the study. If it is confirmed that the participant will permanently discontinue study intervention following discussion with the TIMI Hotline, an Early Termination visit should be performed, which should include assessments of patient-reported outcomes, physical activity (6MWT), and laboratory assessments. In addition, a follow-up visit (F/U1) should be completed approximately 28 days and another follow-up visit (F/U2) should be completed ideally no more than 94 days for the Main Cohort (Cohort A)/Cohort C/Cohort D, and ideally no more than 75 calendar days for the open-label, PK cohort (Cohort B), after discontinuing study intervention primarily for the purpose of assessing resolution of any treatment-related AEs. See the [SoA](#) for data to be collected at the time of discontinuation of study intervention and follow-up for any further evaluations that need to be completed.

Again, it is important to first contact the TIMI Hotline before classifying a subject as ‘Discontinued from Study Intervention’ and completing an Early Termination visit.

In the event of discontinuation of study intervention, it must be documented on the appropriate CRF/in the medical records whether the participant is discontinuing further receipt of study intervention or also from study procedures, posttreatment study follow-up, and/or future collection of additional information.

Follow-Up:

At approximately 28 calendar days (F/U1), and again ideally no more than 94 calendar days for the Main Cohort (Cohort A)/Cohort C/Cohort D and ideally no more than 75 calendar days for the open-label, PK cohort (Cohort B) (F/U2) after discontinuation of study intervention, participants should return to undergo review of concomitant treatments, vital signs, and assessment for resolution of any treatment-related AEs. Participants continuing to experience AEs at this point following discontinuation of treatment will continue to be followed at least every 4 weeks until resolution or determination, in the clinical judgment of the investigator, that no further improvement is expected. If the unresolved AE is considered by the investigator as possibly related to or associated with ADA formation, the participant will be asked to return for drug concentration and ADA blood sampling at up to 3-month intervals, until the last follow-up of the AE.

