1.3. Schedule of Activities

The SoA table provides an overview of the protocol visits and procedures. Refer to the [STUDY ASSESSMENTS AND PROCEDURES](#) section of the protocol for detailed information on each procedure and assessment required for compliance with the protocol.

All study assessments and procedures conducted on scheduled dosing visits should be completed prior to study intervention administration, unless otherwise specified. The investigator may schedule visits (unplanned visits) in addition to those listed in the SoA table, in order to conduct evaluations or assessments required to protect the well-being of the participant.

Table 1. Study Schedule of Assessment for the Main Cohort (Cohort A), Cohort C, and Cohort D

Visit Identifier See abbreviations in Appendix 11 .	SV1	SV2	Week 0	Week 4	Week 8	Week 12	Week 16	Week 20	Week 22 EoT	Week 24 F/U1	Week 32 F/U2	Flex PK/PD visit*	Early Term	Notes
Study day	No earlier than -56	No later than -15, when feasible	1	29	57	85	113	141	155	169	225			SV2 may commence following confirmation of eligibility from SV1 assessments. SV2 should commence at a minimum of 15 days prior to first dose, when feasible. Study day relative to start of dosing (Day 1). F/U1 and F/U2 and/or the Flexible PK/PD visit may be conducted by qualified personnel at the participant's home or current residence.
Visit Window (days)	N/A	N/A	N/A	±3	±3	±3	±3	±3	±2	±3	±7			
Informed consent	X													See Section 10.1.3 .
Screen for eligibility	X	X												See Section 5.1 and Section 5.2 . Screening will be conducted in at least 2 visits (SV1 and SV2). See Section 8.1.1 .
Investigator reported assessment of eligibility for Inclusion Criteria #5a	X													See Section 8.1.1 . Performed after participant completion of KCCQ-23 at SV1.
Demographics	X													
Randomization			X											See Section 6.3 .
Medical history	X	X												
Physical examination		X	X						X					See Section 8.3.1 . Brief physical examinations to be completed before administration of study intervention.

Table 1. Study Schedule of Assessment for the Main Cohort (Cohort A), Cohort C, and Cohort D

Visit Identifier See abbreviations in Appendix 11 .	SV1	SV2	Week 0	Week 4	Week 8	Week 12	Week 16	Week 20	Week 22 EoT	Week 24 F/U1	Week 32 F/U2	Flex PK/PD visit*	Early Term	Notes

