7.2.1. Withdrawal of Consent

Participants who request to discontinue study intervention will remain in the study and must continue to be followed for protocol-specified follow-up procedures. The only exception to this is when a participant specifically withdraws consent for any further contact with them or persons previously authorized by the participant to provide this information. Participants should notify the investigator in writing of the decision to withdraw consent from future follow-up, whenever possible. The investigator should inform the TIMI Hotline of any potential withdrawal of consent.

A participant may withdraw from the study at any time at their own request. If a participant withdraws from the study, they may request destruction of any remaining samples taken and not tested, and the investigator must document any such requests in the site study records and notify the sponsor accordingly.

If the participant withdraws consent for disclosure of future information, no further evaluations should be performed and no additional data should be collected. The sponsor may retain and continue to use any data collected before such withdrawal of consent. Lack of completion of all or any of the withdrawal/early termination procedures will not be viewed as protocol deviations so long as the participant's safety was preserved.

The withdrawal of consent should be explained in detail in the medical records by the investigator, as to whether the withdrawal is only from further receipt of study intervention or also from study procedures and/or posttreatment study follow-up, and entered on the appropriate CRF page. In the event that vital status (whether the participant is alive or dead) is being measured, publicly available information should be used to determine vital status only as appropriately directed in accordance with local law.

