8.2.5. Clinical Outcomes

Details of deaths occurring during trial follow-up will be collected in the CRF and/or separate adjudication packages. Investigators will classify deaths as cardiovascular or non-cardiovascular according to the primary cause of death, which is the underlying disease or injury that initiated the train of events resulting in death. In addition, all deaths will be

adjudicated by a blinded adjudication committee consisting of independent external experts. Cardiovascular death includes:

- Death resulting from an acute myocardial infarction
- Sudden cardiac death
- Death due to heart failure or cardiogenic shock
- Death due to stroke
- Death due to cardiovascular hemorrhage
- Death due to other cardiovascular cause (eg, pulmonary embolism, peripheral artery disease)

Worsening heart failure events occurring during the trial (after randomization) will be collected in the eCRF and/or separate adjudication packages. Worsening heart failure events include both heart failure hospitalizations and urgent heart failure visits. Please refer to the eCRF completion requirements for the clinical criteria needed to classify an event as a heart failure hospitalization or urgent heart failure visit. All investigator-reported worsening heart failure events will be adjudicated by a blinded adjudication committee consisting of independent external experts.

The occurrence of potential clinical outcome will trigger the compilation of a dossier that includes anonymized supporting medical record information that will be sent to the adjudication committee.

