8.4.1. Time Period and Frequency for Collecting AE and SAE Information

The time period for actively eliciting and collecting AEs and SAEs ("active collection period") for each participant begins from the time the participant provides informed consent, which is obtained before undergoing any study-related procedure and/or receiving study intervention, through and including the time of the final planned follow-up visit, except as indicated below, after the last administration of the study intervention.

Follow-up by the investigator continues throughout the active collection period and until the AE or SAE or its sequelae resolve or stabilize at a level acceptable to the investigator.

When a clinically important AE remains ongoing at the end of the active collection period, follow-up by the investigator continues until the AE or SAE or its sequelae resolve or stabilize at a level acceptable to the investigator and Pfizer concurs with that assessment.

For participants who are screen failures, the active collection period ends when screen failure status is determined.

If the participant withdraws from the study and also withdraws consent for the collection of future information, the active collection period ends when consent is withdrawn.

If a participant permanently discontinues or temporarily discontinues study intervention because of an AE or SAE, the AE or SAE must be recorded on the CRF and the SAE reported using the CT SAE Report Form.

Investigators are not obligated to actively seek information on AEs or SAEs after the participant has concluded study participation. However, if the investigator learns of any SAE, including a death, at any time after a participant has completed the study, and they consider the event to be reasonably related to the study intervention, the investigator must promptly report the SAE to Pfizer using the CT SAE Report Form.

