#### **3.3.14.3. Total number of days alive and out of the hospital over 22 weeks**

The total number of days each participant is alive and out of the hospital (DAOH) over the 22 weeks will be calculated:

- For participants alive, lost to follow-up or withdrawal, at Week 22:
  - 'time on study' = time from randomization to Week 22, or to time lost-to-follow-up or withdrawal
  - 'hospitalization time' = sum of all the durations in hospital during the participant's 'time on study'
  - DAOH = 'time on study' – 'hospitalization time'
- For participants who die before Week 22:
  - 'time on study' = time from randomization to Week 22 (Day 155)
  - 'hospitalization time' = sum of all the durations in hospital during the participant's 'time on study'
  - DAOH = 'time on study' – 'hospitalization time' – number of days from the date of death to Week 22

Additionally, the number of days alive and out of the hospital divided by the number of days of study participation (%DAOH) will be calculated:

$$\% \text{ DAOH} = 100 * (\text{DAOH} / \text{'time on study'}).$$

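### For participants who stop study drug early but stay in the study, DAOH, %DAOH and the 22-week HF event rate count days after the last planned visit as alive, out of hospital and event-free

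*Protocol*

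**What the plan says.** Protocol 7.1 gives a participant in Cohorts A, C or D who permanently stops drug an Early Termination visit and F/U1 at about 28 days. It then says that "another follow-up visit (F/U2) should be completed ideally no more than 94 days for the Main Cohort (Cohort A)/Cohort C/Cohort D" after discontinuation. Only participants with continuing adverse events are followed beyond that, at least every 4 weeks. Section 7.1 also says "Note that discontinuation of study intervention does not represent withdrawal from the study", and 7.2.1 keeps such participants in the study for the follow-up procedures that the protocol specifies. Active AE and SAE collection (8.4.1) runs "through and including the time of the final planned follow-up visit". For clinical outcomes, 8.2.5 says "Worsening heart failure events occurring during the trial (after randomization) will be collected in the eCRF and/or separate adjudication packages", but gives no contact schedule for participants off drug.

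For participants who do not die before Week 22, SAP 3.3.14.3 defines time on study for DAOH as "time from randomization to Week 22, or to time lost-to-follow-up or withdrawal". SAP 3.3.14.1 uses the same stopping points, plus death, for days of study participation. That is the denominator of the worsening-HF event rate, which is then scaled to 154 days. SAP 6.3 applies the censored analysis set by default, and SAP 4 treats data after last dose +31 days as missing in that set. SAP 5.2.7 applies the same +31-day cut-off to cumulative incidence.

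**The concern.** A participant who stops drug early and completes F/U2 before Day 155 is not lost, not withdrawn and not dead. None of the SAP's stopping points applies, so the clock runs on to Week 22. No planned visit covers the time after F/U2. A hospital stay or HF event in that time may go unrecorded, while its days still count in full in DAOH and in the rate denominator. Participants still on drug are seen through Week 22.

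Observation therefore depends on whether and when drug was stopped. If early stopping differs by arm, the arm with more of it tends to look better on DAOH, %DAOH and the event rate for a reason unrelated to treatment.

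**Working it through.** **Inputs.** Protocol Table 1 puts the six doses, Week 22, F/U1 and F/U2 on study days "1 29 57 85 113 141 155 169 225", with windows of ±3 days at Week 20 and ±7 at F/U2. Protocol 9.5 assumes 15% discontinuation and has 380 participants on 300 mg or placebo in Cohort A.

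**Reproducing the 94 days.** Last dose to F/U2 is 225 − 141 = 84 days; adding the windows, 84 + 7 + 3 = 94, as stated. The same sum for Cohort B is 155 − 85 + 3 + 2 = 75, also as stated. So 84 is the nominal interval and 94 the ideal maximum.

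**Who is affected.** F/U2 falls before Day 155 only if discontinuation is dated before Day 155 − 94 = 61, or 155 − 84 = 71.

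**Days not covered** = max(0, 155 − anchor day − 84 or 94). The protocol does not say which date counts as discontinuation, so three anchors are shown.

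| Last dose | F/U2 if anchored at last dose | Gap: last dose | Gap: next missed dose (+28) | Gap: last dose +31 |
|---|---|---|---|---|
| Day 1 | Day 85–95 | 60–70 | 32–42 | 29–39 |
| Day 29 | Day 113–123 | 32–42 | 4–14 | 1–11 |
| Day 57 | Day 141–151 | 4–14 | 0 | 0 |
| Day 85 or later | Day 169 or later | 0 | 0 | 0 |

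**Share of person-time.** Assume that stops are spread evenly over the six doses. The mean gap per stopper is largest for last dose with 84 days, (70 + 42 + 14)/6 = 21.0, and smallest for last dose +31 with 94 days, (29 + 1)/6 = 5.0. At 15% discontinuation:
- largest: 0.15 × 21.0/154 = 2.0%
- smallest: 0.15 × 5.0/154 = 0.5%

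The range is 0.2–0.7% at 5% discontinuation and 0.8–3.4% at 25%. Spreading the stops over the first five doses only gives 0.6–2.5% at 15% (0.15 × 6.0/154 to 0.15 × 25.2/154).

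**Headcount, upper end.** If all of the 15% stop drug only, evenly over Days 1–154, the affected share is 60/154 to 70/154 of stoppers. That is 0.15 × 39.0% = 5.8% to 0.15 × 45.5% = 6.8% of participants, or 22–26 of 380.

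**Effect on one participant** (assumed: 10 hospital days or one HF event observed, anchor at last dose). With the clock run to Week 22, %DAOH is (154 − 10)/154 = 93.5% and the 22-week rate is 1.00. With the clock ended at F/U2:
- last dose Day 1 (84–94 days observed): %DAOH 88.1–89.4%, rate 1.83–1.64
- last dose Day 29 (112–122 days): %DAOH 91.1–91.8%, rate 1.38–1.26
- last dose Day 57 (140–150 days): %DAOH 92.9–93.3%, rate 1.10–1.03

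**Censored set.** The cut-offs at last dose +31 are Days 32, 60, 88, 116 and 144 for a last dose on Days 1, 29, 57, 85 and 113. If events after the cut-off are removed and the denominator still runs to Day 155, the credited time grows to 123, 95, 67, 39 and 11 days.

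**The case against.** The strongest reply is that the SAP already excludes these days. Section 6.3 defaults to the censored set, whose cut-off comes before F/U2, and the clinical-outcome section names no other set. That would answer the point if the denominators stopped at the same date. SAP 3.3.14.1 and 3.3.14.3 do not say so, and applying the set to events alone makes the mismatch larger.

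The other side is right to limit several stronger readings that a reader might infer:
- **All 22-week outcomes are affected.** They are not. Cumulative incidence is censored at last dose +31 days (SAP 5.2.7). The Cox section (5.2.8) states no censoring rule of its own. In the win-ratio code, the survivor with the shorter first time variable loses; if that variable is follow-up time, short follow-up is penalised.
- **The composite logistic model codes these participants as having no event.** SAP 5.2.6 says only that missing values are not imputed; the coding of an event-free participant with short follow-up is unstated.
- **Events after F/U2 are never collected.** This is an inference. Protocol 8.2.5 collects HF events during the trial, 7.2.1 keeps the participant in the study, and the 94 days is an ideal. The documents show only that no contact is specified.
- **22–26 participants is an estimate.** Protocol 9.5 does not split the 15% by reason. Deaths, losses and withdrawals already have their own rules, so the number who stop drug only is smaller by an unknown amount.

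**Conclusion.** The point stands as a minor one. For stops before about Day 61–71, the literal definitions of DAOH, %DAOH and the 22-week HF event rate count days that no planned visit covers as alive, out of hospital and event-free. The gap is up to 70 days for one participant, but only about 0.5–2.0% of person-time overall. That share rests on the protocol's 15% rate, on stops spread evenly over the doses, and on the range of anchors shown; the documents give neither the timing of stops nor the share who stop drug only. These endpoints are tertiary, have no estimand, and are summarized descriptively (SAP 6.3.14.3 and 6.3.14.4). No primary or secondary result is touched.

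**What to change.** In SAP 3.3.14.1 and 3.3.14.3, end days of study participation and time on study at the earlier of Week 22 and the date outcome status was last ascertained. When the censored set is used, end them at last dose +31 days. Numerator and denominator then cover the same period. Reconcile this wording with SAP 4, 5.2.7 and the default in 6.3, and define the date of discontinuation from which F/U2 is counted. In SAP 5.2.6 or 6.3.14.1, state that event-free participants not ascertained to Week 22 are not coded as having no event. Leave the +31-day censoring of cumulative incidence as it is.

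Optionally, add to Protocol 7.1 and Table 1 a Week 22 telephone contact for participants in Cohorts A, C and D whose F/U2 falls before Day 155, asking about vital status, hospitalizations and urgent HF visits. SAP wording stops the false credit; only the contact recovers the information.

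The cost is a few lines of SAP text and, with the contact, one call for at most about 6–7% of participants. Where status is not ascertained, follow-up is somewhat shorter. Absolute DAOH then also falls for these participants because the clock is shorter, as it already does for those lost or withdrawn, so %DAOH is the measure to interpret.
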